7.1.1 Pre-Clinical Experience

In our laboratories and those of others, systemic immunization using DCs co-cultured with uncharacterized tumor homogenate [105], whole tumor RNA [106], unidentified peptides eluted from tumor cells by gentle acid washing [107], or a distinct peptide encompassing the tumor-specific epidermal growth factor receptor variant type III (EGFRvIII) mutation [108], have been shown to induce humoral and cell-mediated systemic immune responses and to prolong the survival of rodents with brain tumors.

In our laboratory [105], inbred VM/Dk mice received three or four weekly intraperitoneal injections of autologous bone marrow-derived DCs transiently co-cultured with tumor homogenate. The homogenate was derived from a syngeneic murine astrocytoma cell line derived from a spontaneously occurring astrocytoma in the inbred VM/Dk mouse strain. Splenocytes from

mice immunized in this way were able, *in vitro*, to lyse the astrocytoma cell line that was used to generate the tumor homogenate. They were also able to lyse other astrocytoma cell lines derived from the same inbred mouse strain, but they had no effect against syngeneic fibroblasts. Similarly, these immunized mice also demonstrated a significantly increased antibody titer against the astrocytoma cell line used to generate the homogenate. In addition, mice immunized with DCs transiently co-cultured with tumor homogenate that were subsequently challenged with a lethal dose of this astrocytoma cell line intracerebrally were found to have a median survival >160% longer than those immunized with DCs cultured without tumor homogenate ($P = 0.016$). In addition, 50% of the mice treated with the tumor homogenate-supplemented DCs survived long-term without any evidence of tumor growth and also survived a rechallenge of tumor cells indicating that a sustained antitumor immune response had been established. These findings are especially significant in light of the fact that the astrocytoma cell line used is known to secrete the immunosuppressive agent transforming growth factor- β (TGF- β) which is secreted by most human gliomas [109-113].

In another report from our laboratory [106], C57BL/6 mice received three weekly intraperitoneal injections of autologous bone-marrow derived DCs co-cultured with tumor homogenate or whole tumor RNA derived from the poorly immunogenic B16F10 melanoma cell line. Standard *in vitro* cytotoxicity assays again revealed that splenocytes harvested from mice immunized with DCs transiently co-cultured with either tumor-derived homogenate or whole tumor RNA were able to lyse B16F10 melanoma cells but not unrelated tumor cells from the same MHCbackground. In this experiment, mice immunized with autologous bone-marrow derived DCs co-cultured with tumor homogenate or whole tumor RNA increased median survival by > 233% ($P = 0.0006$) and 48% ($P = 0.0001$), respectively, relative to mice immunized with DCs co-cultured with tumor homogenate or whole tumor RNA derived from an unrelated tumor with the same MHC background. In addition, 8/13 (61.5%) in the specific homogenate group and 4/10 (40%) in the specific RNA group survived beyond the endpoint of the study without evidence of tumor. Immunization of mice with pre-existing tumors with specific tumor homogenate also demonstrated the potency of this immunization approach by increasing survival by 62.5% relative to controls. In these mice, an inflammatory infiltrate composed of mononuclear cells and polymorphonuclear leukocytes was identified, only in mice treated with DCs co-cultured with tumor homogenate that matched the intracerebral tumor challenge.

In a recent report from another laboratory [107], the survival of tumor-bearing rats injected subcutaneously with autologous bone marrow-derived DCs co-cultured with peptides eluted from tumor cells with a gentle acid wash was significantly prolonged compared to tumor-bearing rats receiving equivalent numbers of DCs co-cultured with peptides acid-eluted from normal astrocytes ($P < 0.05$). Median survivals in these groups were 35 and 22 days, respectively. In addition, three of the twelve rats (25%) treated with DCs co-cultured with acid-eluted tumor peptides remained alive at the end of the experiment. In addition, immunohistochemical analysis of five animals from each group in this experiment documented an increased peritumoral and intratumoral infiltration of CD8+ T-cells, and to a lesser extent CD4+ T cells and macrophages, in the group treated with DCs co-cultured with peptides acid-eluted from tumor cells when compared to controls.

Under IND-12839, we have used labeled DCs with ^{111}In and used single-photo emission computerized tomography (SPECT) imaging to track the migration to the VDLNs. This work was published in *Nature* [118].

There is a vast amount of experience with both the safety and efficacy of immunotherapy targeting human CMV [37]. Vaccination specifically against CMV has effectively and without toxicity, reduced the risk of viral infection and transmission to fetuses in clinical trials [61, 65, 69-72]. Adoptive T-cell therapy has been used to safely and successfully protect against CMV reactivation in myelodepleted bone marrow transplant patients [43, 44, 46, 119]. In addition, T cell-mediated immunotherapy has proven highly effective in the treatment of CMV-associated disease within the central nervous system [47] and in the treatment of acute CMV infections [44, 48]. Tumors associated with other human Herpesviruses, such as Epstein-Barr virus-associated lymphoma, including tumors within the CNS, have also been effectively treated and even large tumors have been cured by immunotherapy [49-52, 54, 120]. The pp65 minimal epitope peptide (495-503) was shown to be safe in doses up to 10mg in hematopoietic stem cell transplant patients, with grade 1 adverse events being most commonly reported in approximately 10-15% of the participants and was successful in expanding CMV reactive T-cells [121].

7.2 Study Purpose/Rationale

Our Overall Goal in this project is to extend our substantial pre-clinical and clinical findings and verify these in a larger cohort. We hypothesize that CMV pp65-loaded DCs given with Td and GM-CSF to a larger group of patients with TMZ-induced lymphodepletion will confirm our previous findings by inducing significant DC migration to draining lymph nodes, producing high levels of Chemokine (C-C motif) ligand 3 (CCL3) and polyfunctional CMV pp65-specific T cells systemically, and confirming extra-ordinary PFS and OS.

We will conduct a larger Phase 2 trial of CMV pp65-loaded DC vaccination in patients with GBM. We will confirm our observations from smaller studies, in order to determine if a Phase 3 trial is warranted and to estimate patient numbers that might be required. Patients with CMV positive, newly-diagnosed GBM will receive serial vaccines with CMV pp65-loaded DCs with Td and GM-CSF vaccine site pre-conditioning after standard of care treatment with concurrent external beam radiation and TMZ chemotherapy. Only patients that are methylguanine-DNA methyltransferase (MGMT) unmethylated will be enrolled because adjuvant TMZ shows very little benefit in that population so it can be avoided after the initial treatment that induces transient lymphodepletion.

Next, we will also confirm predictive biomarkers of survival. In our prior studies, DC migration to draining lymph nodes and systemic CCL3 and CMV pp65-specific polyfunctional T cells predicted PFS and OS. Here we will collect samples to confirm these predictive biomarkers prospectively.

Strikingly, Td-treated patients had systemically enhanced DC migration to VDLNs and significantly improved PFS and OS compared to controls (median PFS 18.5 vs 10.8 months, OS 25.7 vs 18.5 months) with half the Td cohort living > 44.1 months from diagnosis. Our murine studies corroborated that Td pre-conditioning systemically enhanced DC migration and suppressed tumor growth. In the proposed clinical study, we aim to enhance the migration of CMV pp65 RNA-pulsed DCs with Td and adjuvant GM-CSF and will assess if increased migration using these strategies can be predictive of patient survival outcomes.

8 OBJECTIVES AND ENDPOINTS

Table 1. Objectives and Endpoints

	Objective	Endpoint	Analysis
Primary	Determine if Td preconditioning of pp65 loaded DC vaccination with GM-CSF extends overall survival.	Median survival from initiation of dose intensive adjuvant temozolamide.	See Section 15.5
Secondary	Assess the association between migration of CMV pp65 RNA-pulsed DCs with GM-CSF to site-draining inguinal lymph nodes after Td pre-conditioning and subsequent survival. (PLEASE NOTE: With Protocol v.20220204, this objective has been removed as it was already addressed in a previous study.)	For survival after vaccine 4, the hazard ratio associated with a 1 unit increase in migration, defined as the maximum percentage of ^{111}In -labeled DCs reaching inguinal nodes during the 48 hours after the 4 th vaccination.	See Section 15.6.1
Secondary	Assess the association between CCL3 measured post-Td pre-conditioning and subsequent survival.	For survival after vaccine 4, the hazard ratio associated with a 1-unit increase in CCL3 measured post-Td pre-conditioning at vaccine 4.	See Section 15.6.2
Secondary	Assess the association between fold changes in T cell polyfunctionality and subsequent survival.	Mean fold change from baseline in the frequency of pp65 antigen-specific CD8 ⁺ T cells producing three or more cytokines (IFN γ , CCL3, IL-2, TNF α , CD107a) at leukapheresis 2 $14 \pm (4)$ days after vaccine 3. Mean fold change from baseline in the frequency of pp65 antigen-specific CD8 ⁺ T cells producing three or more cytokines (IFN γ , CCL3, IL-2, TNF α , CD107a) at vaccine 6. For survival after vaccine 4, the hazard ratio associated with a 1-fold increase in the frequency of pp65 antigen-specific CD8 ⁺ T cells producing three or more cytokines (IFN γ , CCL3, IL-2, TNF α , CD107a).	See Section 15.6.3
Secondary	Assess whether T _{Reg} levels remain low without adjuvant temozolamide.	Maximum mean peak increase from vaccine 1 in percent T _{Reg} of CD4 ⁺ T cells.	See Section 15.6.4
Secondary	Assess the safety of DI-TMZ treatment followed by DC vaccination.	Proportion of patients who experience unacceptable toxicity.	See Section 15.6.5
Exploratory	Assess the association CCL3 levels and migration.	Mean fold change in CCL3 between pre- and post-Td pre-conditioning. Correlation between CCL3 change from fold change in CCL3, and migration.	See Section 15.7.1
Exploratory	Assess the association between pp65-specific polyfunctional CD8 ⁺ T cells and increased DC migration.	Correlation between fold change from baseline (pre-vaccine 1) in polyfunctional CD8 ⁺ T cells and migration.	See Section 15.7.2
Exploratory	Assess the association between pp65-specific polyfunctional CD8 ⁺ T cells and increased serum CCL3.	Correlation between fold change in polyfunctionality and fold change in CCL3	See Section 15.7.3

9 INVESTIGATIONAL PLAN

9.1 Study Design

Approximately 64 patients with resected, newly-diagnosed WHO Grade IV glioma who are CMV+ and in which the MGMT is not methylated will be accrued to this study before standard of care radiation therapy (RT) and concurrent TMZ, with the goal of treating 48 patients with dose-intensified temozolomide and pp65 loaded dendritic cell vaccine after completion of standard RT and TMZ.

All enrolled patients will undergo a leukapheresis after resection for harvest of peripheral blood lymphocytes (PBLs) for generation of DCs. Patients will then receive approximately 6 weeks of standard of care radiation therapy (RT) and concurrent TMZ at a standard targeted dose of 75 mg/m²/d (please see Package Insert uploaded in electronic IRB for standard therapy). Patients should start RT within approximately 7 weeks of surgery. [PI discretion can be used in this situation to allow patients outside of this window to enroll.] Patients who either experience progressive disease during radiation, are dependent on steroid supplements above 2 mg/day at time of first vaccination, are unable to tolerate TMZ, or whose DCs fail to meet release criteria will be withdrawn from the study and replaced. For patients whose initial leukapheresis yields less than 3 vaccines, repeat leukapheresis may be obtained a minimum of 2 weeks from the previous leukapheresis (and may be repeated as needed) if pre-apheresis blood work is within the Apheresis Center's parameters and as long as this does not cause a significant delay in treatment for the patient. At the post-RT clinic visit the patient's MRI and blood work is evaluated before starting a single post-RT cycle of dose intensified TMZ (100 mg/m²/day for 21 days). On day 23 (\pm 2 days) of the cycle, patients will receive the first of 3 pp65 DC vaccines. DC vaccines #1-3 will be given every two weeks (\pm 2 days). All patients will receive up to a total of 10 DC vaccines, with vaccines administered every 35 days (\pm 7 days) after the third vaccine, given bilaterally at the groin site unless progression occurs with no further cycles of TMZ. DC vaccines will be given intradermally (i.d.) and divided equally to both inguinal regions. Before the first DC vaccination, patients will receive 0.5 mL of Td (tetanus and diphtheria toxoids adsorbed) intramuscularly into the deltoid muscle to ensure adequate immunity to the tetanus antigen. The Td vaccine will be obtained through Duke Investigational Chemotherapy Services (ICS) Pharmacy. Patients will undergo leukapheresis again for immunologic monitoring with specific assessment of baseline antigen-specific cellular and humoral immune responses if needed for further DC generations 14 (\pm 4) days after vaccine #3. Prior to pp65 DC vaccination #4, (3 \pm 1) weeks after leukapheresis 2 the vaccine site will receive a pre-conditioning intradermal injection of Td (1 flocculation unit (Lf), in 0.3 mL of saline for a total of 0.4 mL).

As part of standard care for these patients, upon tumor progression, participants may undergo stereotactic biopsy or resection. As this is not a research procedure consent will be obtained separately. However, if tissue is obtained, it will be used to confirm tumor progression histologically and to assess immunologic cell infiltration and pp65 antigen escape at the tumor site. No other treatment intervention is allowable while on study, unless the patient needs bevacizumab at 7.5 mg/kg IV approximately every 3 weeks per the "Special Considerations" in Section 9.1.3.

9.1.1 Definition of Unacceptable Toxicities

Toxicities will be graded according to the National Cancer Institute Common Toxicity Criteria of Adverse Events (NCI CTCAE) version 5 criteria. An unacceptable toxicity is defined as any Grade 3 or greater toxicity that is possibly, probably, or definitely attributed to the pre-conditioning agent Td or pp65 DC vaccine that does not resolve to baseline in 2-3 weeks; any Grade 3 hypersensitivity reactions or autoimmune toxicity requiring steroids or hormone replacement; and is not due to progressive disease, or any life-threatening event not attributable to concomitant medication, co-morbid event, or disease progression. Rules for monitoring unacceptable toxicity are provided in Section 15.6.5.

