13 SAFETY MONITORING AND REPORTING

13.1 Adverse Events

An AE is any untoward medical occurrence in a subject receiving pre-conditioning or the study vaccine and which does not necessarily have a causal relationship with this treatment. For this protocol, the definition of AE also includes worsening of any pre-existing medical condition. An AE can therefore be any unfavorable and unintended or worsening sign (including an abnormal laboratory finding), symptom, or disease temporally associated with the use of the DCs, whether or not related to use of the DCs. Abnormal laboratory findings without clinical significance (based on the PI's judgment) should not be recorded as AEs. But, laboratory value changes that require therapy or adjustment in prior therapy are considered adverse events.

Adverse events will be collected from the time of administration of the first DC vaccine through 1 month after the subject's last vaccine, all AEs must be recorded in the subject's medical record and adverse events case report form.

AEs will be assessed according to the CTCAE version 5. If CTCAE grading does not exist for an AE, the severity of the AE will be graded as mild (1), moderate (2), severe (3), life-threatening (4), or fatal (5).

Attribution of AEs will be indicated as follows:

- Definite: The AE is clearly related to the study drug
- Probably: The AE is likely related to the study drug
- Possible: The AE may be related to the study drug
- Unlikely: The AE is doubtfully related to the study drug
- Unrelated: The AE is clearly NOT related to the study drug

Attribution of AEs will be determined for each study intervention individually (pp65 DC vaccine, pre-conditioning agent [Td], TMZ, bevacizumab).

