13.2 Adverse Events of Special Interest

Adverse events will not be collected until the patient has received the DC vaccine, unless they are considered an Adverse Event of Special Interest related to the leukapheresis procedure. Only these special interest adverse events will be collected prior to the DC vaccine, all other events occurring prior to DC vaccine administration will not be recorded or monitored.

Special Interest Adverse Events that may occur during the leukapheresis procedure include:

- Allergic Reaction
- Anaphylaxis
- Pre-syncope
- Syncope
- Vasovagal reaction

Special Interest Adverse Events that may occur after the procedure, but may still be related to leukapheresis include:

- Vascular Access Complications
- Venous Injury

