15.2 Analysis Sets

All patients who initiate dose-intensified TMZ after completion of standard of care RT and TMZ will be included in the primary efficacy analyses, and toxicity summaries.

Subject to the availability of data, analyses of correlative objectives will include all or some of the patients who undergo vaccine 4. For analyses of migration, the first 16 patients who reach vaccine 4 will undergo migration analyses. For CCL3, all patients who reach vaccine 4 will be included in statistical analyses. For analyses of polyfunctionality, the first 24 patients who reach vaccine 4 will be considered.

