15.6.5 Secondary Objective #5: Toxicity

Objective	Assess the safety of DI-TMZ treatment followed by DC vaccination.																		
Analysis Set	All patients who initiate DI-TMZ treatment.																		
Outcome	Proportion of patients with unacceptable toxicity as defined in Section 9.1.1.																		
Hypothesis	The toxicity profile associated with DI-TMZ followed by DC vaccination is safe.																		

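### The protocol contradicts itself on whether adverse events in the DI-TMZ cycle are recorded, and the Section 15.6.5 proportion measures Td/vaccine safety after DI-TMZ rather than safety of the whole regimen

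*Combined protocol and SAP*

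**What the plan says.** **Aim and population.** The hypothesis in Section 15.6.5 reads "The toxicity profile associated with DI-TMZ followed by DC vaccination is safe", and its analysis set is "All patients who initiate DI-TMZ treatment". Section 15.2 agrees: patients who start DI-TMZ "will be included in the primary efficacy analyses, and toxicity summaries".

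**Outcome.** The outcome is the proportion with unacceptable toxicity as defined in Section 9.1.1. That definition has three limbs:
- Grade 3 or worse toxicity "possibly, probably, or definitely attributed to the pre-conditioning agent Td or pp65 DC vaccine" that has not returned to baseline in 2-3 weeks.
- Grade 3 hypersensitivity, or autoimmune toxicity needing steroids or hormone replacement, with no attribution to a particular agent required.
- Life-threatening events not explained by concomitant medication, comorbidity or progression.

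**AE record.** Section 13.1 says "An AE is any untoward medical occurrence in a subject receiving pre-conditioning or the study vaccine" and "Adverse events will be collected from the time of administration of the first DC vaccine". Section 13.2 excepts listed leukapheresis events and then states that "all other events occurring prior to DC vaccine administration will not be recorded or monitored". Section 9.1.3 instead places the AE baseline at the clinic visit after RT/TMZ, before DI-TMZ starts, and keeps a summary of all AEs from then on. In Table 4 the row for concomitant medications and AEs is marked in the DI-TMZ column.

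**Attribution.** Section 13.1 also says "Attribution of AEs will be determined for each study intervention individually", and TMZ is one of the interventions it lists.

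**The concern.** DI-TMZ is part of the protocol regimen, with a specified dose and duration (Section 9.1), and it is the first component named in the safety objective. A low proportion under 15.6.5 would be read as evidence that the whole sequence is safe. Yet that proportion does not move with ordinary Grade 3 TMZ toxicity.

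The AE tables by maximum grade ought to supply what the proportion leaves out. Whether they do depends on which section the site follows. Under 13.1 and 13.2, a table covering all DI-TMZ starters would be empty of non-serious events for nearly all of the DI-TMZ dosing period, and nothing in the table would show that the period had not been recorded. Section 7.2 says the trial is meant to help decide whether a Phase 3 trial is warranted, so the safety summary is likely to be carried forward.

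**Working it through.** **1. How much of DI-TMZ precedes AE recording under 13.1 and 13.2.** Inputs from Section 9.1: 21 days of dosing, and vaccine 1 on day 23 ± 2, so on day V from 21 to 25. With day 1 as the first dose and daily dosing, the dosing days before vaccine 1 are min(21, V − 1).
- V = 21: min(21, 20) = 20 days.
- V = 22 to 25: 21 days.

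At least 20 of the 21 dosing days therefore precede the start of recording.

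**2. The AE instructions side by side.**

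| Place | AEs in the DI-TMZ cycle |
|---|---|
| 13.1 | Outside both the AE definition and the collection period |
| 13.2 | Not recorded, leukapheresis events excepted |
| 9.1.3 | Inside: baseline and summary both begin after RT/TMZ |
| Table 4 | Inside: row marked in the DI-TMZ column |
| 15.2, 15.6.5 | Population begins at DI-TMZ, which presupposes a record from then |

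These are all current text, and a site cannot follow all of them.

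**3. Which TMZ events the 9.1.1 proportion can count.**
- Attributed at least possibly to Td or vaccine as well: counted under limb 1 if unresolved.
- Grade 3 hypersensitivity or qualifying autoimmune toxicity: counted under limb 2, even if due to TMZ alone.
- Life-threatening: counted under limb 3, unless TMZ is treated as a concomitant medication. The text does not settle this.
- Any other non-life-threatening Grade 3 or worse event attributed to TMZ alone: not counted.

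**4. The plan's own figures.** Applying the Table A limits after each patient with an exact binomial recursion to 48 patients gives the following probabilities of accrual suspension.

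| True rate | Table B | Recomputed |
|---|---|---|
| 0.05 | 0.036 | 0.036 |
| 0.10 | 0.200 | 0.198 |
| 0.15 | 0.502 | 0.496 |
| 0.20 | 0.784 | 0.779 |
| 0.25 | 0.936 | 0.933 |
| 0.30 | 0.987 | 0.986 |

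The largest gap is 0.006. Table B reproduces, as a function of whatever rate is counted.

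**5. What an unrecorded period would look like.** If events before vaccine 1 are not recorded, the table shows 0 of 48 by construction. Taken at face value, 0 of 48 has an exact 95% upper limit of 1 − 0.025^(1/48) = 7.4%. The documents give no TMZ-only toxicity rate, so the rates below are assumptions.

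| Assumed true rate | Expected patients of 48 | Probability of a genuine zero |
|---|---|---|
| 5% | 0.05 × 48 = 2.4 | 0.95^48 = 0.085 |
| 10% | 0.10 × 48 = 4.8 | 0.90^48 = 0.006 |

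The zero itself is a consequence of the recording rule and is not a finding. The calculation shows only how reassuring the table would look.

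**The case against.** The strongest reply is that the trial tests the vaccine. Sections 9.1.2 and 10.1 identify the study drug as the DC product, and Section 15.1 frames the trial around Td pre-conditioning and GM-CSF. Limiting 9.1.1 to Td and vaccine is then a reasonable choice. Section 15.6.5 cites 9.1.1 openly, and no formal test is attached. This stands: the definition needs no change, only the label on the result.

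The second reply is that the loss is limited, and this stands in part. Section 7.1 describes leukopenia as essentially the only known TMZ toxicity, and Section 7.2 relies on TMZ-induced lymphodepletion. Table 4 schedules CBC and CMP at the DI-TMZ visit and at vaccine 1, so laboratory changes still present at vaccine 1 can be recovered. Immediate SAE reporting (13.3.1), the six-monthly toxicity review and the option to suspend for other safety concerns (15.6.5) remain. TMZ-attributed events starting after vaccine 1 would be recorded. What is not recovered is non-serious, non-laboratory toxicity before vaccine 1, and toxicity in anyone who stops before reaching it.

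A reader might infer three stronger things, none of which the documents support:
- *That the protocol simply leaves DI-TMZ out of the AE record.* Section 9.1.3 and Table 4 say otherwise. The defect is a contradiction.
- *That many DI-TMZ starters are never vaccinated and dilute the proportion.* The 40 patients anticipated in Section 15.6.2 are those reaching vaccine 4, so patients lost between vaccines 1 and 4 were vaccinated. Section 9.1 aims to treat 48 with both DI-TMZ and vaccine. The TMZ-intolerance withdrawal criterion in 12.6.1 names no phase and may refer to TMZ given with radiation.
- *That the stopping rule is miscalculated.* Table B reproduces.

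**Conclusion.** The point holds as a contradiction in the AE window together with a mislabelled safety outcome. If 13.1 and 13.2 govern, at least 20 of 21 DI-TMZ dosing days are missing from an AE record that 15.2 and 15.6.5 use for all DI-TMZ starters. If 9.1.3 and Table 4 govern, the record is complete and only the labelling issue remains. The documents do not say which the site follows.

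Under either reading, the 9.1.1 proportion omits non-life-threatening Grade 3 or worse events attributed to TMZ alone, outside hypersensitivity and autoimmune toxicity. How many patients that involves cannot be derived from the documents; the 5% and 10% rates above are illustrations. The primary survival analysis and the monitoring rule are unaffected. The change should be made, because AEs that were never recorded may be hard to reconstruct later.

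**What to change.** - Amend 13.1 and 13.2 so that AEs are defined and collected from the start of DI-TMZ, matching 9.1.3 and Table 4.
- Restate the 15.6.5 outcome and hypothesis as the safety of Td plus pp65 DC vaccine given after DI-TMZ. Report the proportion in patients with at least one vaccination (group 3 of Section 15.3) as well as in all DI-TMZ starters.
- Add a separate proportion for TMZ-attributed Grade 3 or worse events in all DI-TMZ starters, with lymphopenia shown apart because lymphodepletion is intended. The TMZ attribution this needs is already required by 13.1.
- Leave the 9.1.1 definition and Table A unchanged.

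The cost is wording changes in three sections, two extra summary rows, and about three weeks of added AE recording per patient if the site now follows 13.1 and 13.2. There is little or no added recording if it already follows 9.1.3 and Table 4. Patients already treated under 13.1 and 13.2 would need retrospective chart review; the documents do not say how many there are. Stopping rules and patient management do not change.
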